2.2 Previous Data

Previous studies have evaluated the efficacy of steroid injections as compared to placebo injections in the treatment of trigger finger but no previous studies have compared steroid/lidocaine injections to injections without lidocaine. The aim of this study is to compare post-injection pain and efficacy of trigger finger injection using a combination of lidocaine/corticosteroid versus corticosteroid injection alone or corticosteroid/saline (equal volume). Our hypothesis is that lidocaine causes unnecessary pain upon injection and does not improve the efficacy of the steroid in providing sustained anti-inflammatory benefit. We also seek to determine if volume of injection plays a role in immediate post-injection pain (corticosteroid/saline group).

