1.2 Primary Study Endpoints

- Compare pain and efficacy associated with the three treatment groups.
 - VAS and mean daily pain values

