8.0 Data and Specimen Banking For Future Undetermined Research

8.1 Data and/or specimens being stored – N/A

8.2 Location of storage – N/A

8.3 Duration of storage – N/A

8.4 Access to data and/or specimens – N/A

8.5 Procedures to release data or specimens – N/A

8.6 Process for returning results– N/A**9.0 Statistical Plan****9.1 Sample size determination**

Sample size was determined based on a review of prior studies that used the VAS as the main outcome tool. A total sample size of 221 was determined based on the number needed to detect a difference of 5 mm assuming a standard deviation of 10 mm in the VAS and when also considering a 15 % drop out rate. 221 total patients initially enrolled in the study would account for 64 patients per treatment arm (Corticosteroid only v corticosteroid/lidocaine v corticosteroid/saline). Public Health Sciences will be ensuring accuracy of statistical analyses. Stratification based on perioperative variables of interest will not be necessary in our study. Instead, we will be analyzing these variables via subgroup multivariate analyses at the conclusion of the study.

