9.2 Statistical methods

The daily average pain score (VAS) will be compared between groups using either t-test or Wilcoxon test for each of the 6 days after the operation. Chi-square tests will be used to compare treatment groups for categorical variables (satisfaction, presence of clicking/locking, adverse events). Level of significance will be set at $p < 0.05$.

Secondary statistical analysis will include multivariate analyses to determine which variables such as anatomic location and comorbidities will impact the VAS score or modify the efficacy of injection. These can be accomplished by adding these variables and their interaction with treatment groups in the regression model. As these are secondary analysis, any interesting findings will be subject to validation in future studies.

Any deviations from the previously described statistical plan will be described and justified in a protocol amendment.

All analyses comparing the treatment groups will be conducted on an intention-to-treat basis. Two-tailed tests will be used at all times.

There will be an interim analysis when 50 % of patients (n=111) are enrolled and have completed final visit testing.

10.0 Confidentiality, Privacy and Data Management**10.1 Confidentiality****10.1.1 Identifiers associated with data and/or specimens**

See the Research Data Plan Review Form

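### The sustained-efficacy hypothesis is a claim of no benefit from lidocaine, but section 9.2 plans only difference tests and gives no rule for concluding it

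*Combined protocol and SAP*

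**What the plan says.** Section 2.2 gives a hypothesis in two parts. The first is that lidocaine adds unnecessary pain on injection. The second is that it "does not improve the efficacy of the steroid in providing sustained anti-inflammatory benefit". Efficacy is also in the primary endpoint: section 1.2 reads "Compare pain and efficacy associated with the three treatment groups".

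The analysis is in section 9.2. The VAS score "will be compared between groups using either t-test or Wilcoxon test for each of the 6 days after the operation". For categorical outcomes, "Chi-square tests will be used to compare treatment groups for categorical variables (satisfaction, presence of clicking/locking, adverse events"). The threshold is p < 0.05, and "Two-tailed tests will be used at all times". A secondary regression looks for variables that modify the VAS score or the efficacy of the injection.

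Section 9.1 bases the sample size on "the number needed to detect a difference of 5 mm assuming a standard deviation of 10 mm in the VAS", with 64 patients per arm and 221 enrolled after allowing for 15% dropout. Section 16.0 rounds this to 222, or 74 per arm. No section states an equivalence or non-inferiority hypothesis, a margin, or a rule for judging a confidence interval.

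**The concern.** The two parts of the hypothesis need different evidence. Extra injection pain is a difference, and a two-sided difference test suits it. Absence of added sustained efficacy is not something such a test can establish: p ≥ 0.05 is compatible both with no benefit and with a benefit the trial was too imprecise to detect.

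At stake is the practical message that lidocaine can be left out without losing efficacy, and section 13.2 expects the results to guide treatment. If that message rests on failure to reject, anything that adds noise makes it easier to reach. Missed 6-week calls and a VAS score given verbally by phone in half-point steps (section 7.2.2) are two possible sources.

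**Working it through.** **Inputs.** Difference 5 mm, SD 10 mm, 15% dropout and 64 evaluable per arm (9.1); two-sided 0.05 (9.2); 222 enrolled (16.0). Power is not stated; 80% is assumed because it reproduces the plan's figure. Completers per arm: 222 × 0.85 / 3 = 62.9, so 63; the plan's own figure is 64.

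**The plan's sample size.** Normal approximation: n = 2 × [10 × (1.960 + 0.842) / 5]² = 62.8, so 63 per arm. With the t distribution, power is 79.5% at 63 and 80.1% at 64, so 64 is the t-test size. Then 3 × 64 = 192, and 192 × 1.15 = 220.8, so 221. The design is therefore sized for one two-sided pairwise test of difference.

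**Precision.** With 63 per arm, SE = 10 × √(2/63) = 1.78 mm, and the 95% half-width is t(0.975, 124) × SE = 1.979 × 1.78 = 3.53 mm (3.50 mm at 64). For example, an observed 3 mm advantage for CSL would be non-significant, with an interval from 3 − 3.53 = −0.53 to 3 + 3.53 = 6.53 mm. That interval includes a benefit of 5 mm.

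**Chance of a non-significant result when lidocaine truly helps.** Noncentral t, 124 df, noncentrality d / SE, SD 10 mm, 63 per arm:

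| True benefit d (mm) | P(p ≥ 0.05) |
|---|---|
| 1 | 0.914 |
| 2 | 0.800 |
| 3 | 0.614 |
| 4 | 0.394 |
| 5 | 0.205 (0.199 at 64 per arm) |

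If 5 mm is the benefit that matters, the last row is the one to use. Reading p ≥ 0.05 as no improvement would be wrong about 20% of the time at a true 5 mm benefit. Requiring the 95% interval to exclude 5 mm limits that error to 2.5%.

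**What the same patients could show under an interval rule.** The chance that the upper 95% limit for the benefit is below 5 mm when the true difference is 0 is 0.795 at 63 per arm and 0.801 at 64. The remaining 0.205 includes 0.025 in which CSL is significantly better. So about 0.18 of such trials would be non-significant while the interval still reaches 5 mm, and these are properly inconclusive.

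**Sensitivity.** The documents do not tie the SD of 10 mm to the 6-week score, and they give no margin. The values below are assumptions.

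- SD 15 mm, margin 5 mm, 63 per arm: the chance of excluding the margin at true difference 0 falls to 46%.
- SD 20 mm, same margin and size: 29%. Reaching 80% would need 2 × [20 × 2.802 / 5]², or 252 per arm.
- SD 10 mm, 80% power: a 4 mm margin needs 2 × [10 × 2.802 / 4]², or 99 per arm; a 3 mm margin needs 175.
- Adjusting for two comparisons would need more again.

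**The case against.** The strongest reply is that the misreading is not written down. Section 9.2 nowhere says that a non-significant result will be taken as no improvement, the endpoints are worded as comparisons, and the hypothesis sits in a background section. This stands in part: the fault is a hypothesis without a matching decision rule, not a stated wrong inference. But it is the protocol's only stated hypothesis, and the rule has to be set before results are seen to be credible.

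Four stronger readings are tempting, and the documents do not support them.

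- A reader might infer that non-significance is the only possible support. It is not: the tests are two-tailed, so a significant result with CSL worse would also support the hypothesis. That has a probability of 2.5% in a given comparison if the arms are equal.
- A reader might take 5 mm as a margin already fixed. Section 9.1 gives it as a difference to "detect a difference of 5 mm assuming a standard deviation of 10 mm in the VAS", drawn from earlier VAS studies. It is not linked to 6-week efficacy or called the largest benefit one could forgo.
- A reader might infer that no extra patients are ever needed. That depends on the margin, SD, number of comparisons and true difference assumed.
- A reader might treat CSL versus CSS as the deciding contrast. Section 2.2 names both CS and CSS as comparators and ranks neither.

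The figures above also describe a test that the plan does not explicitly contain. Section 9.2 writes the VAS comparison for six daily scores, whereas section 7.2 collects VAS before injection, at 1 and 10 minutes, and at 6 weeks. Efficacy is primary in section 1.2, effectiveness of the injection is secondary in section 1.3, and a triggering question is asked at 6 weeks too. This limits the numbers to an illustration at the plan's own assumptions, and it is a further reason to name the comparison.

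**Conclusion.** The concern holds for the sustained-efficacy half of the hypothesis only; the injection-pain half is suitably tested. If the arms are similar, the planned analysis can return only a non-significant p-value, and that does not establish absence of benefit. At SD 10 mm and 63 to 64 completers per arm, a true 5 mm benefit would be missed about 20% of the time, and each pairwise 95% interval is about ±3.5 mm.

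The chance of about 80% of excluding a 5 mm benefit with the planned enrolment rests on four assumptions together: a 5 mm margin, SD 10 mm at 6 weeks, one comparison, and a true difference of 0. That the interval should be judged instead of the p-value is firm. Which margin to use, and whether the trial can meet it, is open.

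**What to change.** In section 9.2:

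- Name 6-week VAS as the sustained-efficacy comparison.
- Report the 95% confidence interval for CSL versus CS and for CSL versus CSS.
- State that a non-significant result will be reported as no difference detected, and not as no improvement.
- Conclude no meaningful improvement only if the interval excludes a prespecified margin, with its justification given. The 5 mm in section 9.1 may serve if the sponsor can justify it for this purpose. Otherwise report the result as inconclusive.
- Keep the two-sided difference test for injection pain.

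The cost is about a paragraph of text plus the work of justifying a margin. The downside is that a non-significant result with a wide interval can no longer be reported as support. With a smaller margin or a larger 6-week SD, an inconclusive efficacy result becomes likely at the planned size, and the sponsor should accept that in advance or revisit enrolment.

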2.3 Study Rationale

See study objectives

3.0 Inclusion and Exclusion Criteria

3.1 Inclusion Criteria

- Age: 18 – 90
- Gender: male or female (non-pregnant)
- Clinically diagnosed trigger digit
- Subject is able to provide voluntary, written informed consent
- Subject, in the opinion of the clinical investigator, is able to understand the clinical investigation and is willing to perform all study procedures and follow-up visits.

3.2 Exclusion Criteria

- Age: <18 or >90
- Pregnant or lactating women
- Non-English speaking individuals
- Medication contradictions to lidocaine, corticosteroids and/or saline
- History of multiple drug allergies
- Prior injection or surgery on the affected finger
- Diagnosis of reflex symptomatic dystrophy (RSD) or complex regional pain syndrome (CRPS)
- Open wound

- Inability to provide informed consent

3.3 Early Withdrawal of Subjects

3.3.1 Criteria for removal from study

Patients will be withdrawn from the study for safety reasons including severe adverse reactions, failure of subject to adhere to protocol requirements, or subject consent withdrawal.

3.3.2 Follow-up for withdrawn subjects

If a patient is withdrawn from the study, data collection will be terminated from that time point forward. All prior data collected will be included in the analysis. These subjects will not be replaced, but instead more subjects may need to be enrolled. These new data will be recorded and analyzed as would any other new enrollee. No further follow-up of withdrawn subjects is necessary.

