7.2.3 Study Visit Flowsheet

Screening Visit – Visit 1	6-Week Follow-Up – Phone Call
Enrollment, Randomization, Pre-injection VAS, Injection, Post-injection VAS x 2, objective hand exam (SOC)	VAS, trigger question

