7.3 Duration of Participation

Subjects will only be seen in the clinic site once (time of enrollment in study) and will be contacted via telephone six weeks post-injection.

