7.4.2 Treatment Regimen

The study investigator will perform a single injection using a 25 gauge 1.5" needle. The needle will be inserted at 90 degrees to the skin, 1 cm proximal to the metacarpophalangeal joint flexion crease.

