11.8 Suspension of research

There will be no stopping rules in this study as all medications are FDA approved and safe for patient use.

If a patient, at any point in the course of their treatment demonstrates a significant adverse event related to the study medication, then the adverse event will be addressed.

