21.2 Recording of Adverse Events

All adverse events (serious or non-serious) and abnormal test findings observed or reported to study team believed to be associated with the study drug will be followed until the event (or its sequelae) or the abnormal test finding resolves or stabilizes at a level acceptable to the investigator.

An abnormal test finding will be classified as an adverse event if one or more of the following criteria are met:

- The test finding is accompanied by clinical symptoms
- The test finding necessitates additional diagnostic evaluation(s) or medical/surgical intervention; including significant additional concomitant drug treatment or other therapy
Note: Simply repeating a test finding, in the absence of any of the other listed criteria, does not constitute an adverse event.
- The test finding leads to a change in study drug dosing or discontinuation of subject participation in the clinical research study
- The test finding is considered an adverse event by the investigator.

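### Section 3.3.2 stops data collection for every withdrawn patient whatever the reason; read literally this conflicts with 21.2, and it gives up an already scheduled 6-week score

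*Combined protocol and SAP*

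**What the plan says.** Section 3.3.1 names the grounds for removal, among them "severe adverse reactions, failure of subject to adhere to protocol requirements, or subject consent withdrawal". Two of these are decisions about the patient by the study team; the third is the patient's own decision.

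Section 3.3.2 then applies one rule to all of them: "If a patient is withdrawn from the study, data collection will be terminated from that time point forward". It adds: "No further follow-up of withdrawn subjects is necessary". Data already collected stay in the analysis, and more patients may be enrolled.

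Section 21.2 sets a different rule for safety. Adverse events and abnormal findings "believed to be associated with the study drug will be followed until the event (or its sequelae) or the abnormal test finding resolves" or settles at a level the investigator accepts. It makes no exception for withdrawn patients.

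On treatment and schedule, 7.4.2 says: "The study investigator will perform a single injection". After that one clinic visit, 7.3 says that patients "will be contacted via telephone six weeks post-injection", and the flowsheet in 7.2.3 lists the content of that call as "VAS, trigger question". Section 9.2 says that treatment comparisons follow the intention-to-treat principle.

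**The concern.** There are two separate difficulties.

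- **Safety recording.** A patient removed because of a drug reaction falls under both 3.3.2 and 21.2. One section ends data collection and calls further follow-up unnecessary; the other continues follow-up of the event. The reaction that led to removal would already be on record, but its course and after-effects might not be. Adverse events are a study objective (1.1), a secondary endpoint (1.3) and one of the comparisons named in 9.2.
- **Outcome data.** Removal after a single injection withholds no further study treatment. Its only effect on the data is to drop the 6-week call. That call is the only assessment scheduled after visit 1, and so the only scheduled measure of the lasting benefit in the hypothesis (2.2). If removals for reactions differ between arms, the patients missing at 6 weeks are missing for a reason that may be related to treatment. Enrolling more patients restores the count but not the outcomes of those who were lost.

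**Working it through.** **Sections side by side**, for a patient removed by the investigator for a drug reaction who has not withdrawn consent:

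| Question | 3.3.2 | Elsewhere |
|---|---|---|
| Is the event still followed? | Data collection ends; follow-up not required | 21.2: yes, until resolved or stable |
| Is the 6-week call made? | No | 7.3 and 7.2.3: scheduled for all, silent on removed patients |
| Is any study treatment stopped? | Not addressed | 7.4.2: one injection, already given |

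The conflict rests on 3.3.2 against 21.2. Section 11.8 says of a significant event related to the study medication: "then the adverse event will be addressed". That concerns dealing with the event, not recording it, and is compatible with 3.3.2. Section 11.3 is a general six-week schedule that does not mention withdrawn patients, so it adds little.

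**The plan's own sample size.** Inputs from 9.1 and 9.2: difference 5 mm, SD 10 mm, two-sided 5% level, 15% dropout. Power is not stated; at an assumed 80%, a two-sample t-test needs 64 per arm, which matches 9.1. Then 3 x 64 = 192 and 192 x 1.15 = 220.8, or 221 as stated. Per arm, 64 x 1.15 = 73.6, or 74 as in 16.0. The allowance is 74 - 64 = 10 per arm.

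**Shift in one arm's 6-week mean.** Let x be the proportion of the arm removed and g the mean VAS of removed patients minus that of retained patients. The full-arm mean is (1 - x) x retained mean + x x removed mean, so full-arm mean minus retained mean = x x g. The documents give neither x nor g; all values below are assumptions.

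- x = 2%, g = 10 mm: 0.02 x 10 = 0.2 mm
- x = 5%, g = 20 mm: 0.05 x 20 = 1.0 mm
- any x, g = 0: no shift
- x = 5%, g = -10 mm: 0.05 x (-10) = -0.5 mm

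**Shift in the difference between two arms**, with g = 20 mm in both:

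- 5% and 5% removed: 1.0 - 1.0 = 0
- 5% and 2% removed: 1.0 - 0.4 = 0.6 mm
- 5% and 0% removed: 1.0 - 0 = 1.0 mm

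These shifts are not set against the 5 mm target, because 9.1 ties that target to no time point.

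**Precision.** 0.02 x 74 = 1.5 and 0.05 x 74 = 3.7 patients per arm. Both are below 10, although that allowance must cover every kind of dropout. If the full 15% of 74 (11.1) were lost, 62.9 would remain, with t-test power of 79.5%. Recovering a tenth of them (1.1) gives 64.0 and 80.2%. The effect on power is slight either way.

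**The case against.** The strongest reply is that the sections can be read together. Section 3.3.2 is the general rule for study data, and 21.2 is the specific rule for drug-associated events. Saying that follow-up is not necessary does not forbid it. Section 11.3 also has adverse events collected as they occur, and 11.5 has them reviewed as they occur. This reading is workable, and it means that the protocol should not be described as abandoning patients with severe reactions. What remains is that 3.3.2 refers to data collection without limiting it to outcome data, so a coordinator following its words would stop.

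A reader might also infer that the 6-week comparison is biased. The documents do not support that. They give no removal rates by reason and no 6-week scores, and the shift could be zero or go either way. The only VAS test named in 9.2 covers six days, so no specified 6-week VAS result can be shown to move. The 1- and 10-minute scores will usually have been taken before removal and are kept.

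Nor does 9.2 promise outcome collection after withdrawal, and nothing moves withdrawn patients out of their randomised arm. The stop rule therefore fits poorly with intention-to-treat without formally breaching it.

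Finally, the recoverable group is narrow. Ending collection when consent is withdrawn is no defect. After one injection, there is little left to adhere to beyond the surveys and the call. Some removed patients may not be reachable or willing. All of this limits the gain but does not give a reason for the blanket rule.

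**Conclusion.** The point holds as a wording conflict to be reconciled and an avoidable loss of data. It is not a demonstrated bias or safety failure. Section 3.3.2 has no exception by reason, and for patients removed because of a drug reaction its literal wording conflicts with 21.2. It also gives up the 6-week VAS and trigger answer from randomised patients who may still consent to contact.

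The size cannot be derived from the documents. With assumed removals of 2% to 5% and assumed gaps of -10 to 20 mm, the worked single-arm shifts run from -0.5 to 1.0 mm, and the worked shifts between arms from 0 to 1.0 mm. The effect is probably small. No loss of planned power is claimed. The case for acting rests on the low cost of the change and the clear wording problem.

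**What to change.** - Reword 3.3.2 so that only a patient's withdrawal of consent to further contact ends data collection.
- For patients removed by the investigator who still consent and can be reached, keep the already scheduled 6-week call and analyse them in their randomised arm.
- Record the reason for each removal, so that investigator removal and consent withdrawal can be told apart.
- State how the sentence in 3.3.2 that makes further follow-up unnecessary is to be reconciled with 21.2 for drug-associated events.

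The cost is a protocol wording amendment, a check that the consent wording allows the contact (the consent pages are not in the documents reviewed), and a few telephone calls that were already in the schedule.

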4.0 Recruitment Methods

4.1 Identification/Recruitment of subjects

Subjects will be identified as part of their initial or routine evaluation by one of the study investigators in the Bone & Joint Institute.

4.2 Recruitment materials – N/A

4.3 Eligibility/screening of subjects

Adult patients presenting to the Bone & Joint Institute will be evaluated as part of standard of care. Those subjects meeting eligibility requirements will be presented with the opportunity to participate in the research study by a member of the research team.

